## 1. Summary

Primary Objective:	To evaluate the change in patient Oral Health-related Quality of Life (OHRQoL) from wearing a cobalt chrome (CoCr) removable partial denture (RPD) to wearing the Solvay Dental 360™ polymer Removable Partial Denture (RPD) for 8 weeks.
Secondary Objectives:	
 
• To investigate the difference in health of the abutment teeth following the use of the polymer Removable Partial Denture (RPD) as compared to the Cobalt chrome (CoCr) Removable Partial Denture (RPD) as assessed by the plaque score and gingival bleeding index
 
• To investigate the difference in whole plaque score following the use of the polymer Removable Partial Denture (RPD) as compared to the Cobalt Chrome (CoCr) Removable Partial Denture (RPD)
 
• To investigate the health of the mucosal bearing areas of the polymer Removable Partial Denture (RPD) as compared to the Cobalt Chrome (CoCr) Removable Partial Denture (RPD)
 
• To investigate framework hygiene (disclosing), probing depths, and abutment tooth mobility
 
• To investigate the professional (operator) based outcomes for the fit, function, occlusion and aesthetics
 
• To investigate the patient assessment of the comfort, aesthetics and chewing ability after the polymer Removable Partial Denture (RPD) and Cobalt Chrome (CoCr) Removable Partial Denture (RPD)
 
• To determine the denture preference of each patient
 

Indication:	Partial edentulism with no active periodontal disease or caries
Investigational Design:	
Cohort study conducted in the United States & United Kingdom to assess Oral Health Related Quality of Life (OHRQoL) in patients receiving the study polymer Removable Partial Denture (RPD) as compared to their baseline Cobalt Chrome (CoCr) Removable Partial Denture (RPD) Oral Health Quality of Life (OHRQoL).
 
Subjects who are current wearers of a Cobalt Chrome (CoCr) Removable Partial Denture (RPD) will complete an Oral Health Related Quality of Life (OHRQoL) instrument, the Oral Health Impact Profile (OHIP) questionnaire, at baseline and again after wearing their prescribed polymer Removable Partial Denture (RPD) for 8 weeks

Inclusion/exclusion criteria:	
Inclusion criteria:
 
Adults from age 18 upwards:
 
 
With the absence of 4 or less teeth per saddle, excluding third molars
 
Partial denture in one arch only
 
With previous denture wearing experience, and Cobalt Chrome (CoCr) Removable Partial Denture (RPD) fitted in the previous 60 months and the patient is currently and routinely wearing the denture
 
With a stable oral health in terms of absence of disease activity affecting the periodontium, dental hard tissues (caries), pulp and the structural/aesthetic integrity of restored teeth
 
With at least 1 posterior natural tooth occlusal stop (molar or premolar)
 
Class I, Class II and Class III (Kennedy's Classification)
 
Occlusal spacing (static and dynamic) around clasp assembly including the occlusal rest
 
 
Exclusion criteria:
 
 
Patients requiring extensive treatment prior to the provision of a removable partial denture (RPD)
 
Patients with active primary disease; caries, periodontal disease or symptoms of pulpal or apical pathology to the remaining teeth
 
Patients with irreversibly compromised structural/aesthetic integrity of restored teeth that cannot be restored as part of the provision of treatment.
 
Patients with an opposing Removable Partial Denture (RPD). Removable Partial Denture (RPD) to only be in one arch and must oppose a full denture or a dentate arch which provides a stable occlusal relationshipCanines are NOT to be replaced with the Removable Partial Denture's (RPDs). Patients must have their natural canines present
 

Number of Subjects:	40 subjects Maximum of 3 sites (US and UK)
Target Population:	Patients aged 18 Years and older
Follow-up:	Enrollment, standard of care prosthodontic visits for prescribing Removable Partial Dentures (RPDs), 3 study follow-up visits during 8 week polymer Removable Partial Denture (RPD)
Length of Investigation:	wearing period Up to 6 months

Primary Endpoint:	Change in Patient Oral Health Related Quality of Life (OHRQoL) after wearing the polymer Removable Partial Denture (RPD) and Cobalt Chrome (CoCr) Removable Partial Denture (RPD)
Secondary Outcome	
 
Comparison of the health of the abutment teeth during/following the use of the polymer Removable Partial Denture (RPD) as compared to Cobalt Chrome (CoCr) Removable Partial Denture (RPD)
 
Operator assessment of the adaptation of the polymer frame, adaption of the tissue base areas and their relationship to the frame adaptation, functional evaluation, aesthetic assessment and oral health assessment of abutment teeth and the periodontium
 
Patient-centered assessment of comfort, aesthetics and chewing ability before and after construction of the new denture by a 5 point Likert scale
 
Oral health parameters associated with the Removable Partial Denture (RPD) abutment teeth (probing depths and mobility) and Removable Partial Denture (RPD) mucosal bearing areas
 
Evaluation and photographic documentation of the Polymer Removable Partial Denture (RPD) for cracks, fractures, permanent deformation or other signs mechanical failure
 

Test Device/ Procedure:	Removable partial polymer prosthesis to replace missing teeth
Clinical Performance Assessments:	To investigate patient overall Oral Health Related Quality of Life (OHRQoL) with the polymer Removable Partial Denture (RPD) as compared to the Cobalt Chrome (CoCr) Removable Partial Denture (RPD).
Statistical Analysis:	A one-sample T-test will be used to assess the change in patient overall Oral Health Related Quality of Life (OHRQoL) using the Cobalt Chrome (CoCr) Removable Partial Denture (RPD) and Polymer Removable Partial Denture (RPD). A non-inferiority boundary will be used.

## 2. Background and Rationale

Partial edentulism is prevalent, especially in adults 65 and older. Periodontal disease is one of the major causes of loss of teeth, along with caries (cavities) and trauma. Tooth loss subsequently affects individual overall oral health and quality of life. Removable partial dentures (RPDs) are commonly made for people with few to several missing teeth as a cost-effective method for replacing teeth. In addition to being more affordable than fixed partials and dental implants, Removable Partial Dentures (RPDs) are a less invasive treatment and may be easier to maintain by the users. Removable partial dentures (RPDs) allow individuals to regain oral function and health and bilateral occlusal support (Wismeijer, 2011). Several factors affect satisfaction and quality of life of those with Removable Partial Dentures (RPDs), including aesthetics, comfort, phonetics, mastication and retention.

The framework of Removable Partial Dentures (RPDs) can be made out of different materials, including metal, acrylic and polymer, all comprised of different properties. A common framework material is cobalt chromium (CoCr), a rigid, nonprecious metal alloy. Other framework materials include titanium and non-metal materials such as medical grade arylketone polymer (AKP). Polymer Removable Partial Dentures (RPDs) provide an alternative to individuals with metal allergies or sensitivity. The plastic replacement teeth and gingival/alveolar complex sit on the framework. The removable partial denture (RPD) stabilises the remaining dentition and unites the entire arch.

Computer Aided Design (CAD) and Computer Aided Manufacturing (CAM) is utilised in the fabrication of the polymer Removable Partial Dentures (RPDs). The 3D software provides increased accuracy and faster turn-around time in providing removable dentures to patients.

Careful attention is paid to denture base fit and extensions, functional elements of speech and mastication, occlusion, and appearance/soft tissue support. Post-placement evaluation is done to assess patient comfort, function and aesthetics. Fitting adjustments are made as necessary.

When evaluating or comparing treatment options, variables such as survival rate and longevity of the prostheses, and frequency of complications have been regarded as the most important outcomes for clinicians; however, the social and psychological impacts of treatment, cost effectiveness, benefit, and utility are more important factors from the patient's perspective (Furuyama, 2011).

Patient's satisfaction or dissatisfaction with their partial dentures is an important part of the removable partial denture (RPD) treatment. Patients adapt to partial dentures individually, depending on their prior experience, expectations, emotional and general health status, as well as on the status of the oral cavity. For some patients, satisfaction with partial dentures relates primarily to comfort and ability to masticate, while aesthetics and retention are more important for others (Dubravka, 2000).

In addition, the condition, number, and alignment of the abutment teeth; the gingival, periodontal, and mucosal tissue health; the type of the construction and denture support; and the material and denture base shape are also common reasons for patient dissatisfaction. Other factors dependent on the patient may be the quality of the denture-supporting area and oral mucosa, influence of the surrounding muscles on the denture flanges, viscosity of saliva, patient's age and ability to get used to the denture, state of the abutments, condition of the other teeth in the mouth, relation between the horizontal and vertical dimensions of occlusion, hygiene habits, diet, presence of chronic diseases, position of the patient's teeth in the mouth, and quality of the removable appliance. (Reference: Treatment Outcomes with Removable Partial Dentures: A Comparison

Between Patient and Prosthodontist Assessments). Therefore, a thorough initial oral exam is a critical step in the preparation for the insertion of the Removable Partial Denture (RPD).

There is a need to assess the impact of polymer removable partial dentures (RPDs) on overall patient oral health and quality of life. Based on previous studies and literature, Removable Partial Denture (RPD) alternatives, such as polymer Removable Partial Dentures (RPDs), should be considered and assessed, with Oral Health Related Quality of Life (OHRQoL) validated instruments and patient satisfaction surveys.

## 2.1. Background

### Background of Polymers and use in Denture Frames

The family of polymers known as arylketone polymers (AKP) are high performance polymers that have proven useful in a variety of demanding engineering applications, often as a lightweight alternative to metals. Because of their physical and chemical properties, Arylketone is considered a high-performance polymer with utility in fabrication via traditional melt processing and used successfully in the aerospace, chemical processing, and medical devices markets. Arylketone Polymers (AKP) also exhibit biocompatibility and have been used successfully in a variety of medical applications, including orthopaedic implants and instrumentation. The arylketone polymers have long been considered viable replacements for metals in medical applications as demonstrated by numerous global regulatory approvals. Arylketones offer weight reduction over metals for devices such as surgical retractors and orthopaedic implants. Polymers such as PEEK have been used extensively to replace cobalt chrome and titanium in orthopaedic implants to reduce the effects of stress shielding (Najeeb S., 2015). These polymers are also radio-lucent, thereby eliminating the possibility of imaging artifacts. Polymers may also offer significant cost savings and eliminate the risk of metal sensitivity.

Due to these combinations of properties, arylketones represent promising alternatives for metals in denture frames. Their customisation to patient needs, via either conventional melt processing or machining of fabricated forms, enables dentists and dental labs to optimally customise each frame to the patient with a material that has a safe history in medical devices. There are currently several polymeric products on the market in the United States and Europe which are thermoplastic materials used for the manufacture of full and partial removable dentures and implant overdentures. Many of these are formed into milling blanks which enable the dentist and dental labs to customise the design of the denture frame for each patient using standard CAD/CAM milling techniques.

They have also been tested and evaluated for biocompatibility and strength according to internationally recognised standards. These include ISO 7405:2008 Dentistry — Evaluation of biocompatibility of medical devices used in dentistry and ISO 20795-1:2013 Dentistry – Base polymers – Part 1: Denture base polymers.

## 2.2. Risk/Benefit Analysis

Arylketone polymers provide an alternative to metal and acrylic denture frames that have previously been used in various medical device applications and have completed full biocompatibility testing.

There are no additional risks to the patient for participating in the study that he/she would not otherwise encounter with standard denture frame assessment and fitting. Standard procedures for

a removable partial denture includes an oral exam, impressions of the jaws, wax bite block, trial insertion of the framework and teeth, fitting and placement of the denture frame, followed by a final review visit.

The public will benefit from the study results that will help to refine the use of polymer removable partial dentures. This will help aid clinicians in the selection of materials to optimise their clinical outcomes of treatment. Data acquisition includes non-invasive collection methods before and after the fitting of the polymer denture frame. The goal of this study is to obtain data on patient centered outcomes on the Oral Health Related Quality of Life (OHRQoL) in patients wearing arylketone polymer (AKP) Removable Partial Dentures (RPDs). The results of this study will advance the design, fabrication and fitting of the polymer Removable Partial Denture (RPD) to further benefit the partially edentulous population. This will help aid clinicians in the selection of materials to optimise their clinical outcomes of treatment.

### **3. Objectives**

#### **3.1. Hypothesis**

Patient Oral Health-related Quality of Life (OHRQoL) after wearing the Solvay Dental 360™ polymer Removable Partial Denture (RPD) is non-inferior to patient Oral Health-related Quality of Life (OHRQoL) after wearing a cobalt chrome (CoCr) Removable Partial Denture (RPD).

#### **3.2. Primary Objective**

To evaluate the change in patient Oral Health-related Quality of Life (OHRQoL) from wearing a cobalt chrome (CoCr) removable partial denture (RPD) to wearing the Solvay Dental 360™ polymer Removable Partial Denture (RPD) for 8 weeks.

#### **3.3. Secondary Objectives**

The secondary objectives are:

- To investigate the difference in health of the abutment teeth following the use of the polymer Removable Partial Denture (RPD) as compared to the Cobalt chrome (CoCr) Removable Partial Denture (RPD) as assessed by the plaque score and gingival bleeding index.
- To investigate the difference in whole plaque score following the use of the polymer Removable Partial Denture (RPD) as compared to the cobalt chrome (CoCr) Removable Partial Denture (RPD).
- To investigate the health of the mucosal bearing areas of the polymer Removable Partial Denture (RPD) as compared to the Cobalt Chrome (CoCr) Removable Partial Denture (RPD).
- To investigate the framework hygiene (disclosing), probing depths, and abutment tooth mobility.
- To investigate the professional (operator) based outcomes for the fit, function, occlusion and aesthetics.

- To investigate the patient assessment of the comfort, aesthetics and chewing ability after the polymer Removable Partial Denture (RPD) and Cobalt Chrome (CoCr) Removable Partial Denture (RPD).
- To determine the denture preference of each patient.

### **3.4. Primary Endpoint**

Change in patient Oral Health Related Quality of Life (OHRQoL) after wearing the polymer Removable Partial Denture (RPD) and Cobalt Chrome (CoCr) Removable Partial Denture (RPD).

### **3.5. Secondary Endpoint**

Secondary outcome measures will be included to detect health of the abutment teeth and plaque accumulation, using the whole plaque score and gingival bleeding index of abutment teeth.

- The comparison of the health of the abutment teeth during/following the use of the polymer Removable Partial Denture (RPD) as compared to the Cobalt Chrome (CoCr) Removable Partial Denture (RPD) as assessed by the arch plaque score and gingival bleeding index.
- Operator assessment of the adaptation of the polymer frame, adaption of the tissue base areas and their relationship to the frame adaptation, functional evaluation, aesthetic assessment and oral health assessment of abutment teeth and the periodontium.
- Oral Health parameters associated with the Removable Partial Denture (RPD) abutment teeth (probing depths and mobility) and Removable Partial Denture (RPD) mucosal bearing areas.
- Patient-centered assessment of the comfort, aesthetics and chewing ability before and after construction of the new denture by a 5 point Likert scale.
- Evaluation and photographic documentation of the Polymer Removable Partial Denture (RPD) for cracks, fractures, permanent deformation or other signs of mechanical failure.

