12.1 General Considerations

Continuous measures will be summarized with sample size, mean, median, standard deviation, minimum and maximum; categorical measures will be presented with the counts and percentages of subjects in each category.

The date of enrollment will be considered study day 1.

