12.2 Analysis Populations

The primary endpoint will be analyzed among all subjects with an overall score reported on the OHIP questionnaire for both the Cobalt Chrome and Polymer Frame.

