12.6 Secondary Analysis

All secondary endpoints will be assessed for all subjects with available data. No formal statistical hypothesis testing will be performed. All objectives will be summarized descriptively as described in section 12.1.

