12.6.2.1 Endpoint Definition

The second secondary endpoint is the health of the abutment teeth during/following the use of the polymer RPD as compared to the CoCr RPD.

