12.6.3.1 Endpoint Definition

The third secondary endpoint is the operator assessment of the adaptation of the polymer frame, adaptation of the tissue base areas and their relationship to the frame adaptation, functional evaluation, aesthetic assessment and oral health assessment of abutment teeth and the periodontium.

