12.6.5.1 Endpoint Definition

The fifth secondary endpoint is the operator assessment of the adaptation of the polymer frame, adaptation of the tissue base areas and their relationship to the frame adaptation, functional evaluation, aesthetic assessment and oral health assessment of abutment teeth and the periodontium.

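### Does the SAP leave mechanical failure of the polymer denture, a declared secondary endpoint, without an analysis?

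*Protocol*

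**What the plan says.** The last item in Protocol 3.5 is "Evaluation and photographic documentation of the Polymer Removable Partial Denture (RPD) for cracks, fractures, permanent deformation or other signs of mechanical failure". The synopsis repeats it among the secondary outcomes ("cracks, fractures, permanent deformation or other signs mechanical failure"), and Protocol 7.2–7.3 schedules the check at Visits 6, 7 and 8.

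The SAP arranges its secondary analyses under seven objectives, 12.6.1 to 12.6.7, each with an endpoint definition. Some definitions repeat: "The second secondary endpoint is the health of the abutment teeth during/following the use of the polymer RPD as compared to the CoCr RPD" restates the first, and "The third secondary endpoint is the operator assessment of the adaptation of the polymer frame" is matched by "The fifth secondary endpoint is the operator assessment of the adaptation of the polymer frame". Cracks, fractures and deformation appear in none of them.

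Two general provisions sit above that list. SAP 12.6 opens with "All secondary endpoints will be assessed for all subjects with available data". SAP 12.1 states that "categorical measures will be presented with the counts and percentages of subjects in each category".

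Protocol 8.1 treats device deficiencies, durability included, as a category of their own and requires them to be reported. SAP 12.9 plans a listing and summary of adverse events, and SAP 12.10 does the same for protocol deviations. Neither names device deficiencies.

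**The concern.** Whether the frame stays intact is an obvious thing to ask of a new denture material. If the SAP leaves out one declared endpoint while carrying over all the others, some of them twice, it is natural to suspect that the result could go unreported or be summarised in whatever form suits it after the fact.

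Two consequences seem possible. A subject who leaves because the frame broke might be missing from a Visit 8 summary, so that the failures that matter most are not counted. And a frame that cracks without harming the patient or ending participation is neither an adverse event nor a discontinuation, so no listing is expressly planned for it.

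**Working it through.** **Endpoint by endpoint.** Protocol 3.5 has five items. Set against the SAP definitions:

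- abutment-tooth health: SAP 12.6.1.1 and 12.6.2.1
- operator assessment: SAP 12.6.3.1 and 12.6.5.1
- oral health parameters: SAP 12.6.4.1
- patient Likert ratings: SAP 12.6.6.1
- mechanical failure: none

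The seventh definition, 12.6.7.1, serves denture preference and has no counterpart in Protocol 3.5. So 2 + 2 + 1 + 1 + 1 = 7 definitions cover four of the five items. The omission is real.

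**Where it comes from.** The SAP follows the seven objectives of Protocol 3.3. Mechanical failure is an endpoint without an objective there, and Protocol 12.1.4 does not mention it either. A document built objective by objective would miss it with no intention to leave it out.

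**Whether the plan still reaches it.** The opening sentence of SAP 12.6 covers all secondary endpoints, and this is one of them by Protocol 3.5. Presence or type of failure is categorical, so SAP 12.1 supplies the format. Protocol 7.3 supplies the visits. The population is all subjects with data; the restriction in SAP 12.2, "The primary endpoint will be analyzed among all subjects with an overall score reported on the OHIP questionnaire" for both frames, applies to the primary endpoint only. Together these give a count and percentage at each of Visits 6, 7 and 8.

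**Whether the enumerated outputs are a closed list.** They are incomplete elsewhere too. SAP 12.6.5 defines operator assessment to include adaptation and function but names only aesthetics as the reported output. SAP 12.6.4 has framework hygiene in its objective but not among the reported variables. Absence from the enumeration is therefore weak evidence that an endpoint was abandoned.

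**Attrition.** Protocol 12.2 plans 40 enrolled with 10% attrition: 40 × 0.10 = 4 lost and 40 − 4 = 36 remaining. Under Protocol 10.1, subjects withdrawn before receiving the device are replaced and those withdrawn afterwards are not, so about 40 frames are delivered and about 4 might lack a Visit 8 evaluation. That is a planning figure, not a bound. Three things limit the effect:

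- nothing confines the summary to Visit 8, so a failure seen at 1 or 4 weeks is counted at that visit;
- Protocol 10.1 asks for the planned assessments at withdrawal where possible;
- SAP 12.3 summarises reasons for discontinuation.

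**Whether a denominator of all delivered frames would be better.** Suppose, as an illustration, one failure is seen and 36 frames are evaluated. The rate is 1/36 = 2.8% among those evaluated and 1/40 = 2.5% among those delivered. The second figure is lower only because four unexamined frames are counted as sound.

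**Precision.** With no failures, the exact two-sided 95% upper limit is 1 − 0.025^(1/n): 8.8% for n = 40 and 9.7% for n = 36. This shows how little about 40 frames can say about a rare failure under either denominator. It does not measure an error in the plan, and the documents give no benchmark failure rate to compare with.

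**Device deficiencies.** Protocol 8.1 has the investigator record a deficiency on the adverse event form or another suitable form in the CRF, and report it to the sponsor within 24 hours. Some deficiencies without harm may therefore reach the SAP 12.9 listing. The SAP does not say so, but the information is collected.

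**The case for a change.** The best argument for a change is that the general cover is thin. A single sentence reaches this endpoint. The sentence in SAP 12.6 that gives the method speaks of objectives, and mechanical failure belongs to none. Every enumerated objective states what is reported and at which visits; this endpoint has no such text, no subject-level rule and no denominator. In a post-market device study, one table and one listing from data already collected would cost almost nothing.

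The textual facts stand. A reader who wants the cumulative number of frames with any failure by Visit 8, or a listing of deficiencies without an adverse event, will not find either promised. Adding them would be tidy.

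What does not stand is the step from unspecified to unreported or wrong. The endpoint is purely descriptive, so no test, error rate or success criterion depends on how it is tabulated. A cumulative count would collect failures already observed, which the visit tables also show, but it would not recover frames nobody examined. Dividing by all delivered frames would introduce a small downward bias of its own unless the unevaluated frames were shown separately.

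**Conclusion.** The concern identifies a true omission in the SAP's enumeration: one of five declared secondary endpoints has no subsection. It does not call for a change. SAP 12.6 and 12.1, read with Protocol 3.5 and the visit schedule, already lead to counts and percentages at Visits 6, 7 and 8, and a competent analyst would fill in the table layout sensibly. Followed as written, the plan produces no wrong figure, test or conclusion.

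The practical size is small: about 4 of 40 frames might lack a Visit 8 evaluation under the planned attrition, with earlier visits and withdrawal assessments covering part of that. The primary OHIP comparison is unaffected.

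This rests on two assumptions: that the CRFs, which are not among the documents, record the mechanical evaluation in a form that can be tabulated at each visit, and that the general sentence in SAP 12.6 is applied to every endpoint in Protocol 3.5.
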